6.5.3. Follow-Up for Immune-Related Adverse Events

An AE with a potential immunologic etiology, or an immune-related AE, may be defined as an AE consistent with an immune phenomenon associated with study drug exposure after all other etiologies have been eliminated. Immune-related AEs may be expected based on previous experience with parsaclisib and other drugs (eg, idelalisib) that inhibit PI3K δ . Special attention should be paid to AEs that may be suggestive of potential immune-related AEs. Suspected immune-related AEs should be discussed with the medical monitor when possible. Participants should receive appropriate supportive care measures as deemed necessary by the treating investigator. Suggested supportive care measures for the management of drug-related AEs with potential immunologic etiology are outlined in Table 9. For each AE, attempts should be made to rule out other causes, including but not limited to bacterial or viral infection, which might require specific supportive care.

6.5.4. **COVID-19**

Infection with SARS-CoV-2, the coronavirus that causes COVID-19, is more frequent and severe in patients with hematologic dysfunction (Jee et al 2022). The presence of hematologic malignancy, baseline neutropenia and lymphopenia, B-cell depletion, and other factors have been identified as risk factors for loss of humoral immunity to COVID-19, poor vaccine response, viral persistence, and severe disease (Lee et al 2022, Lyudovyk et al 2022, Shree et al 2022). Targeting B-cell function, proliferation, and survival with various therapies are current strategies for improving the outcome of several hematologic malignancies. Pi3K-delta inhibition with parsaclisib alone or in combination with other therapies, which may also suppress humoral immunity, has the potential to negatively impact SARS-CoV-2 infection risk, vaccine effectiveness, recovery from COVID-19, and disease severity (Cheson 2022). Investigators and participants participating in trials of parsaclisib, alone or in combinations, need to be aware of these potential risks and consider the local standards of care and available therapies for disease prevention, vaccination (see Section 6.7.1.3), and infection management of COVID-19.

6.5.5. Criteria for Permanent Discontinuation of Study Drug

The occurrence of unacceptable toxicity not caused by the underlying disease will require that the study drug be permanently discontinued. Unacceptable toxicity is defined as follows:

- The occurrence of an AE that is related to study drug that, in the judgment of the investigator or the sponsor's medical monitor, compromises the participant's ability to continue study-specific procedures or is considered to not be in the participant's best interest
- Adverse events that reoccur and/or persist after reduction to 1 mg QD.
- Persistent AE requiring a delay of therapy for more than 21 days unless a greater delay has been approved by the sponsor.
- Specific AEs requiring permanent discontinuation as described in Table 9.

See Section 7.1.2 for discontinuation procedures.

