6.5.1. Criteria and Procedures for Dose Interruptions and Adjustments of Study Drug

Safety concerns should be discussed with the sponsor immediately upon occurrence or awareness to determine if the participant should continue or discontinue study treatment.

Dose modifications are allowed in the study. Dose reductions from 2.5 mg QD to 1 mg QD are allowed after consultation with the medical monitor, if the participant is experiencing an AE assessed as related or of unknown relationship to study drug or for hemoglobin levels in the high end of normal range. Because participants may enter the study with extensive pretreatment and/or hemolysis associated with the primary disease, these dose reduction rules are provided as guidelines (see Table 9). Dose re-escalation is permitted provided the investigator consult with the sponsor medical monitor and the sponsor approves before dose re-escalation.

In some circumstances, it may be necessary to temporarily interrupt treatment with parsaclisib as a result of AEs or laboratory abnormalities that have an unclear relationship to the study drug (see Table 9). Except in cases of emergency, it is recommended that any laboratory findings be confirmed and that the investigator consult with the sponsor medical monitor (or other representative of the sponsor) before temporarily interrupting study drug. Participants who experienced a recurrence of the AEs or laboratory abnormalities upon restarting the study drug may have the study drug permanently discontinued (see Section 7.1.2).

During the study, study treatment may be delayed up to 21 days to allow for resolution of toxicity. Participants may resume treatment if no medical condition or other circumstance exists that, in the opinion of the investigator, would make the participant unsuitable for further participation in the study. The treating investigator should contact the sponsor to discuss the

case of any participant whose treatment has been delayed for more than 7 days before restarting study treatment. See Appendix D for action required for potential Hy's law cases.

Table 9: Guidelines for Interruption and Restarting of Study Drug

ADVERSE EVENT	ACTION TAKEN
Chemistry	
Grade 2 AST and/or ALT is > 3.0 - 5.0 × ULN	Step 1: Interrupt study drug up to 21 days and repeat ALT/AST assessments weekly for up to 3 weeks (local blood collection may be used) or until ALT and/or AST results are < 3.0 × ULN.

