	Step 2: Restart study drug at the same dose and monitor as clinically indicated.
	• If ALT and/or AST result(s) do not decrease to < 3.0 × ULN after 3 weeks of drug interruption, discontinue study drug administration, and the participant will enter the post-treatment follow-up period.
	• If AST or ALT elevation > 3.0-5.0 × ULN reoccurs following restarting study medication administration, repeat Step 1 and then restart study drug at 1 mg QD dose.
	• If AST and ALT > 3.0-5.0 × ULN reoccurs on lower dose, discontinue study drug administration, and the participant will enter the post-treatment follow-up period.
≥ Grade 3 AST and/or ALT is > 5.0 × ULN	Step 1: Interrupt study drug up to 21 days and repeat ALT/AST assessments weekly for up to 3 weeks (local blood collection may be used) or until the toxicity has resolved to <3.0 x ULN (≤ Grade 1).
	Step 2: Restart study drug at a 1 mg dose and monitor as clinically indicated. If reoccurs, discontinue study drug and monitor as clinically indicated and the participant will enter the post-treatment follow-up period.
Hematology	
 Grade 3 ANC (≤ 1.0 × 10⁹/L), unless due to underlying disease Grade 2 platelet count (50 × 10⁹/L to 	Step 1: Interrupt study drug up to 21 days until the toxicity has resolved to ≤ Grade 1 or baseline. For Grade 3 ANC, monitor at least weekly.
$<75\times10^9/L)$	Step 2: Restart study drug at same dose and monitor as clinically indicated. If reoccurs, repeat Step 1 and then restart at the 1 mg QD dose.
	Step 3: If reoccurs at 1 mg dose, discontinue study drug administration and the participant will enter the post-treatment follow-up period.

Table 9: Guidelines for Interruption and Restarting of Study Drug (Continued)

ADVERSE EVENT	ACTION TAKEN		
Hematology (continued)			
 Grade 4 ANC (< 0.5 × 10⁹/L) ≥ Grade 3 ANC with an oral temperature of at least 38.5°C OR with ≥ Grade 3 infection ≥ Grade 3 platelet count (< 50 × 10⁹/L) 	 Step 1: Interrupt study drug up to 21 days until the toxicity has resolved to ≤ Grade 1 or baseline. For ≥ Grade 3 ANC, monitor at least weekly. Step 2: Restart study drug at same dose and monitor as clinically indicated. If reoccurs, repeat Step 1 and then restart at the 1 mg QD dose. 		
	If event persists, discontinue study drug administration and the participant will enter the post-treatment follow-up period.		
Other toxicities			

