Diarrhea/colitis (Grade 1)	Step 1: Treat with antimotility agents (eg, loperamide) and initiate supportive care (see Section 6.5.2). If not improved after 48 hours, treat per guidance for \geq Grade 2.		
Diarrhea/colitis (Grade 2)	Step 1: Interrupt parsaclisib or matching placebo. Perform workup for infection (including CMV, Clostridium difficile , etc) immediately. Initiate or continue supportive care (see Section 6.5.2). Monitor clinical progress closely.		
	Step 2: If improved within 48 hours and/or infection* is confirmed, restart parsaclisib/matching placebo at the same schedule and dose after resolved to ≤ Grade 1 and continue to monitor.		
	*For infectious diarrhea/colitis, follow institutional standard- of-care guidelines and restart parsaclisib/matching placebo according to clinical judgment after resolved to ≤ Grade 1. Consult with medical monitor if needed.		
	Step 3: If not improved within 48 hours and infection is ruled out, start oral steroids or consider IV steroids if participant is being given IV fluids. If no improvement with oral steroids, switch to IV steroids.		
	Step 4: When diarrhea resolves to ≤ Grade 1, continue supportive care and taper steroids according to institutional standard of care. When taper is complete (eg, no steroid or ≤ 10 mg/day prednisone or equivalent) and diarrhea is ≤ Grade 1, restart parsaclisib/matching placebo at the 1 mg QD dose with approval of the medical monitor.		
	Step 5: If Grade 2 diarrhea reoccurs, treat per guidance for diarrhea (≥ Grade 3)/noninfectious colitis.		
	Step 6: If ≥ Grade 2 diarrhea reoccurs a third time, permanently discontinue parsaclisib/matching placebo and the participant will enter the post-treatment follow-up period.		

Table 9: Guidelines for Interruption and Restarting of Study Drug (Continued)

ADVERSE EVENT	ACTION TAKEN
Other toxicities (continued)	
 Diarrhea (≥ Grade 3) Noninfectious colitis (any grade; confirmed or suspected) 	Step 1: Interrupt parsaclisib or matching placebo. Perform workup for infection (including CMV, C. difficile , etc) immediately. Initiate or continue supportive care (see Section 6.5.2). Consider colonoscopy with biopsy for diarrhea ≥ Grade 3 and/or if symptoms suggestive of colitis. Monitor clinical progress closely until resolution.
	Step 2: If infection* is ruled out, start oral steroids or consider IV steroids if participant is being given IV fluids. If no improvement with oral steroids within 48 hours, switch to IV steroids.

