	*For infectious diarrhea/colitis, follow institutional standard- of-care guidelines and restart parsaclisib or matching placebo according to clinical judgment after resolved to ≤ Grade 1. Consult with medical monitor if needed.
	Step 3: When diarrhea/colitis resolves to \leq Grade 1, continue supportive care and taper steroids according to institutional standard of care. When taper is complete (eg, no steroid or \leq 10 mg/day prednisone or equivalent) and diarrhea/colitis is \leq Grade 1, restart parsaclisib or matching placebo at 1 mg QD with approval of the medical monitor. Continue to monitor. If reoccurs, discontinue study drug and the participant will enter the post-treatment follow-up period.
Pneumonitis (Grade 1)	Step 1: Interrupt parsaclisib or matching placebo until the toxicity has resolved.
	Step 2: Restart parsaclisib or matching placebo at the 1 mg QD dose. Monitor as clinically indicated.
Pneumonitis (≥ Grade 2)	Permanently discontinue parsaclisib or matching placebo and the participant will enter the post-treatment follow-up period.
Skin toxicity (eg, rash, pruritus, etc, unless otherwise specified; Grade 2-3)	Step 1: Interrupt parsaclisib or matching placebo until the toxicity has resolved to \leq Grade 1.
	Step 2: Restart parsaclisib or matching placebo at the same dose. If assessed as related to parsaclisib or matching placebo, restart at the 1 mg QD dose.
Exfoliative dermatitis (Grade 1)	Step 1: Interrupt parsaclisib or matching placebo until the toxicity has resolved.
	Step 2: Restart parsaclisib or matching placebo at the 1 mg QD dose. Monitor as clinically indicated.
Exfoliative dermatitis (≥ Grade 2)	Step 1: Interrupt parsaclisib or matching placebo until the toxicity has resolved.
	Step 2: Restart parsaclisib or matching placebo.

Table 9: Guidelines for Interruption and Restarting of Study Drug (Continued)

ADVERSE EVENT	ACTION TAKEN
Other toxicities (continued)	
CMV infection	Participants with CMV viremia without associated clinical signs of CMV infection should be carefully monitored. Consider interrupting parsaclisib or matching placebo for participants with CMV viremia and clinical signs of infection until the infection has resolved. Restart parsaclisib or matching placebo reduce to 1 mg QD dose if approved by the medical monitor.
Varicella zoster infection	Interrupt parsaclisib or matching placebo. Restart parsaclisib or matching placebo only by approval of the medical monitor.

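### When steroid-treated Grade 2 diarrhea recurs on 1 mg, Section 6.5.5 requires stopping study drug, but Table 9 permits one more 1 mg course

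*Protocol*

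**What the plan says.** **The stopping rule.** Protocol Section 6.5.5 requires permanent discontinuation for unacceptable toxicity not caused by the underlying disease. Its second bullet includes in that definition: "Adverse events that reoccur and/or persist after reduction to 1 mg QD". Section 7.1.1 lists unacceptable toxicity under 6.5.5 among the reasons for which study treatment must stop.

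**The diarrhea rows of Table 9.** If Grade 2 diarrhea has not improved at 48 hours and infection is ruled out, steroids are started. After resolution and taper, Step 4 says: "restart parsaclisib/matching placebo at the 1 mg QD dose with approval of the medical monitor". For a recurrence the table says: "Step 5: If Grade 2 diarrhea reoccurs, treat per guidance for diarrhea (≥ Grade 3)/noninfectious colitis". Step 3 of that more severe row, again after resolution and taper, says: "restart parsaclisib or matching placebo at 1 mg QD with approval of the medical monitor. Continue to monitor. If reoccurs, discontinue study drug". The Grade 2 row ends with: "Step 6: If ≥ Grade 2 diarrhea reoccurs a third time, permanently discontinue parsaclisib/matching placebo".

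**The force of the table.** Section 6.5.1 describes the dose reduction rules as guidelines. It also says that participants whose event recurs "upon restarting the study drug may have the study drug permanently discontinued", which is permissive and not tied to a dose.

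**The concern.** For a participant whose steroid-treated Grade 2 diarrhea returns on 1 mg, one section says stop for good and the table says treat and restart at 1 mg. An investigator cannot follow both. Diarrhea and colitis are named risks in Section 2.3, and diarrhea of Grade 2 or higher is an event of clinical interest in Section 9.6. The choice also has consequences later: under Section 6.6, a participant permanently discontinued under 7.1.1 cannot resume parsaclisib in the long-term extension. Amendment 2 closed enrollment but kept participants on treatment and let placebo participants start parsaclisib early (Section 4.1), so first exposures could still occur under this text.

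**Working it through.** There is no plan figure to reproduce. The check traces one participant through Table 9 and compares each step with 6.5.5 and 7.1.1. The count is the number of restarts at 1 mg before study drug must stop; all episodes are noninfectious Grade 2 diarrhea.

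| Sequence | After episode 1 | Episode 2 occurs on | 6.5.5 with 7.1.1 | Table 9 | 1 mg restarts: 6.5.5 / Table 9 | Difference |
|---|---|---|---|---|---|---|
| A. Steroids needed | Step 4: 1 mg | 1 mg | Stop at episode 2 | Step 5, then Step 3 of the Grade 3 or higher row: 1 mg again; stop at episode 3 | 1 / 2 | 2 - 1 = 1 |
| B. Improved within 48 hours, was on 2.5 mg | Step 2: same dose, 2.5 mg | 2.5 mg | Not triggered until episode 3, on 1 mg | Step 5, then Step 3: 1 mg; stop at episode 3 | 1 / 1 | 1 - 1 = 0 |
| C. Improved within 48 hours, already on 1 mg | Step 2: same dose, 1 mg | 1 mg | Stop at episode 2 | Step 5, then Step 3: 1 mg again; stop at episode 3 | 1 / 2 | 2 - 1 = 1 |

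Sequence C is possible because Section 6.5.1 allows reduction to 1 mg for another adverse event or for hemoglobin at the high end of normal.

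Four further readings matter:

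- **Recurrence at Grade 3 on 1 mg.** The participant enters the Grade 3 or higher row directly. Read alone, its Step 3 again permits a 1 mg restart. The general Table 9 row for recurrent Grade 3 toxicity after dose reduction says to discontinue, with exceptions only by sponsor approval. So the table is also at odds with itself here.
- **Infectious recurrence on 1 mg.** Table 9 leaves the restart to clinical judgment after resolution to Grade 1 or less. The second bullet of 6.5.5 has no exception for infection.
- **Step 6.** A third recurrence could mean episode 4. That does not change the count, because Step 3 of the Grade 3 or higher row already stops at the next recurrence, episode 3.
- **Neighboring rows.** For Grade 2 ALT/AST, an elevation that "reoccurs on lower dose, discontinue study drug administration, and the participant will enter the post-treatment follow-up period". The ALT/AST row for Grade 3 or higher and the row for Grade 3 ANC or Grade 2 platelets also stop on recurrence at 1 mg. These rows agree with 6.5.5; the Grade 2 diarrhea row does not.

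**The case against.** The best defense is that the documents already rank the texts: Table 9 holds guidelines, while 6.5.5 and 7.1.1 are mandatory, so stopping prevails. That does suggest the likely intent. But no sentence says so, the table still instructs the restart, and the permissive sentence in 6.5.1 adds a third standard. The last bullet of 6.5.5, on events for which Table 9 requires discontinuation, adds reasons to stop; it does not let Table 9 override the second bullet.

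It is also fair that the extra course cannot happen by default. It needs resolution to Grade 1 or less, a completed taper and medical monitor approval; a delay beyond 21 days needs sponsor approval; and the monitor can declare unacceptable toxicity under the first bullet of 6.5.5. This limits the reach. It does not settle what the monitor should decide, because the second bullet carries no waiver, whereas the third bullet does.

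Two stronger readings are tempting:

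- **A general clash.** Since the second bullet has no grade limit, a reader might infer that it contradicts every instruction in Table 9 to continue through a mild recurrence on 1 mg. The bullet sits within a definition of unacceptable toxicity, and several rows agree with it, so the documents do not establish a general clash. The point rests on diarrhea serious enough to have interrupted treatment.
- **A head count.** A reader might apply the 22.9% diarrhea rate in Section 2.3 to the 13 treated participants. That rate is for any grade, in 35 participants on parsaclisib monotherapy, while the 13 come from a trial with a placebo arm. It says nothing about how many would reach this sequence.

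**Conclusion.** The conflict is real and narrow. In sequences A and C, Table 9 permits one 1 mg course beyond the point where 6.5.5 with 7.1.1 requires permanent discontinuation; in sequence B there is no difference. This assumes that the second bullet applies from the first recurrence on 1 mg, as written, and that Step 5 sends the participant through the whole of the Grade 3 or higher row.

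The documents give no rate for the sequence and do not say whether anyone met it. SAP Section 1 reports 13 participants randomized and treated when the sponsor decided to terminate. A reader might infer that the trial's results are at risk; they are not, because no efficacy or safety tabulation in the SAP is defined by this rule. What is affected is the action taken for an individual participant. This is a minor correction to a safety rule.

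**What to change.** Choose one of two, according to clinical intent.

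1. **If study drug should stop on recurrence at 1 mg:**
   - Reword Step 5 of the Grade 2 row: when diarrhea or colitis of Grade 2 or higher returns on 1 mg QD and infection is excluded, stop permanently; when it returns on 2.5 mg QD, follow the Grade 3 or higher row.
   - Limit the restart in Step 3 of the Grade 3 or higher row to participants not already reduced to 1 mg. Without this, a Grade 2 recurrence would stop while a Grade 3 recurrence could restart. The clinical team should confirm that it also wants this for a first severe episode in someone reduced for another reason.
   - State in Step 6 that the stop is at the third episode.
   - Add to the second bullet of 6.5.5 an exception for confirmed infectious diarrhea managed under Table 9.
2. **If the extra course is intended:** add to the second bullet of 6.5.5 that it applies except where Table 9 gives a different action for that event, and define the third time in Step 6 as the third episode.

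Either is a few sentences in a clarification letter or amendment, with no new data, visits or procedures.

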6.6. Treatment With Parsaclisib During Long-Term Extension

Participants may take a drug holiday one time during the long-term extension. Participants who take a drug holiday may be eligible to resume parsaclisib if they have worsening of wAIHA after the drug holiday. *Note*: Resuming treatment with parsaclisib is not an option for participants who permanently discontinue study treatment for criteria described in Section 7.1.1.

Participants may take a drug holiday during the long-term extension if they meet the following condition:

- Were clinically stable for at least 8 weeks and tolerating treatment before taking a drug holiday.
 - Clinically stable defined as hemoglobin ≥ 10 g/dL with an increase from baseline of ≥ 2 g/dL not attributed to rescue therapy and no worsening or new symptoms of wAIHA

Re-treatment with parsaclisib is available if the study remains open and the participant meets all of the following conditions:

• Experienced worsening of wAIHA defined as a continuing decline in absolute hemoglobin level, a > 1 g/dL decrease in hemoglobin from the prior assessment, or the participant develops new or worsening symptoms of wAIHA after the drug holiday.

AND

• In the opinion of the investigator, resuming treatment with parsaclisib would not pose a significant safety risk to the participant.

Participants will resume parsaclisib at the same dose level and frequency as when they last received parsaclisib. Re-treatment after a drug holiday is permitted one time. Participants will continue study treatment until any of the criteria for permanent discontinuation of study drug are met (see Section 7.1.1). Participants who permanently discontinue study treatment will enter the 12-week post-treatment follow-up visits scheduled every 4 weeks for 12 weeks after the last dose of study drug.

Note: Upon implementation of Protocol Amendment 2, participants receiving parsaclisib who permanently discontinue study drug will enter the post-treatment follow-up period for 1 visit (FUP1/EOS) approximately 4 weeks after the last dose of study drug.

6.7. Concomitant Medications and Procedures

All concomitant medications and treatments (including over-the-counter or prescription medicines, vitamins, vaccines, and/or herbal supplements) must be recorded in the eCRF. Any prior medication received up to 12 weeks before the first dose of study drug and 12 weeks after the last dose of study drug, will be recorded in the eCRF. Any addition, deletion, or change in the dose of these medications will also be recorded. Concomitant treatments/procedures that are required to manage a participant's medical condition during the study will also be recorded in the

eCRF. The medical monitor should be contacted if there are any questions regarding concomitant or prior therapy.

6.7.1. Permitted Medications and Procedures

6.7.1.1. Pneumocystis jirovecii Pneumonia Prophylaxis

All participants will receive a PJP prophylaxis regimen determined by the investigator, which will be locally sourced and reimbursed by the sponsor. The investigator must actively determine if a participant has a known sulfa allergy.

Examples of standard PJP prophylaxis therapies include sulfamethoxazole and trimethoprim, atovaquone, dapsone (diaphenylsulfone) with or without pyrimethamine, and pentamidine (NCCN 2020). (In Japan, diaphenylsulfone and pentamidine are not approved for PJP prophylaxis and thus will not be used.) Due to reports of cross-sensitivity between sulfonamides and dapsone, all participants who have a known or suspected allergy to sulfonamides must receive either inhaled pentamidine or atovaquone for PJP prophylaxis. If inhaled pentamidine or atovaquone are not available, the participants should not be enrolled.

Prophylaxis must be given while participants are receiving study drug and must continue for at least 2 to 6 months after the last dose of study drug.

Further details are available in the Pharmacy Manual.

